3. STUDY OBJECTIVES AND ENDPOINTS

3.1 Study Objectives

3.1.1 Primary Objective

To determine the safety and effectiveness of intravenously infused CAP-1002 in improving clinical outcomes in severely or critically ill patients with COVID-19.

3.1.2 Secondary Objectives

Several exploratory safety and efficacy endpoints will be measured to evaluate the effects of CAP-1002 treatment on the morbidity and mortality of severely or critically ill patients with COVID-19.

3.2 Study Endpoints

- All-cause mortality.
- Ordinal Scale of Clinical Improvement, absolute values and changes from start of treatment to Days 2, 3, 7, 15, and 30.
- Time to a 1-point decrease on the Ordinal Scale of Clinical Improvement from start of treatment.

- Area under the severity versus time curve, where severity is defined by the Ordinal Scale of Clinical Improvement and time is measured from start of treatment to Days 2, 3, 7, 15, and 30.
- Days of supplemental oxygen or mechanical ventilation from start of treatment (up to 90 days).
- First Intensive Care Unit (ICU) discharge
- Days in ICU from start of treatment (up to 90 days).
- Discharge from hospital.
- Days hospitalized from start of treatment (up to 90 days).
- Severity of ARDS as defined by the Berlin criteria, absolute values and changes from start of treatment to Days 2, 3, 7, 15, and 30.
- Cytokine and biomarker results, absolute values and changes from start of treatment to Days 2, 3, 7, 15, and 30.
- Adverse events (AEs) and serious adverse events (SAEs) within 90 days from start of treatment.

4. SAMPLE SIZE

Up to a total of 60 subjects (approximately 30 in each group, CAP-1002 and placebo) will be enrolled and treated in this study. Subjects who are enrolled and randomized but not treated for whatever reason will be replaced for a total sample size of 60 treated subjects. Adequate information is not currently available for formal sample size calculations for this study. The proposed study size reflects a reasonable estimate of subject numbers to support descriptive and correlative assessments involving clinical safety and efficacy information to support further clinical studies.

5. RANDOMIZATION, BLINDING, AND REPLACEMENT OF SUBJECTS

Subjects who meet all enrollment criteria will be randomized to receive either CAP-1002 or placebo (1:1 ratio). Only personnel who have been delegated by the Principal Investigator to randomize subjects may complete the task. Subjects will be randomized in the EDC system approximately 1 to 5 days in advance of their first administration. This lead time is to ensure adequate IP shipping time (see IP Manual for shipping specifications). The master randomization list will be generated per the study Randomization Plan and Specifications in

SAS or comparable software and held in confidence by the unblinded programmer preparing the master randomization list.

This is a double-blind, placebo-controlled trial. Investigational product will be prepared for IV infusion by site personnel who have been appropriately delegated by the Principal Investigator. The IP syringes, once prepared, will appear identical for both treatment groups. However, an investigational pharmacist may be able to differentiate CAP-1002 from placebo on the basis of the opacity of the thawed concentrate observed during IP preparation. For this reason, the investigational pharmacists will have limited interaction with the blinded investigative site personnel.

Site personnel and subjects, staff members at clinical research organizations (CROs), and Capricor personnel will remain blinded to treatment assignment throughout trial conduct. An unblinded DSMB, unblinded statistician, and the DSMB administrator will remain firewalled from any blinded individual involved in trial conduct, services, and/or oversight.

In case of an emergency, the Investigator has the sole responsibility for determining if unblinding of a subject's treatment assignment is warranted. If unblinding is deemed to be necessary, the Investigator should use the mechanism for emergency unblinding outlined in the Manual of Procedures. The date and reason that the blind was broken must be recorded in the source documentation. The Investigator is encouraged to maintain the blind as much as possible. Knowledge of the actual allocation can generally be limited and not disclosed to the subject and/or other trial personnel including personnel at other investigative sites, monitors, Capricor, or other personnel involved in the trial; there should be no written or verbal disclosure of the code in any corresponding subject documents. Unblinding should not necessarily be a reason for termination from the trial.

Replacement of subjects who drop out early will be allowed with sponsor agreement.

6. DEFINITIONS OF SUBJECT POPULATIONS TO BE ANALYZED

- Modified Intent-to-Treat (mITT) and Safety analysis set: All enrolled subjects who were randomized and received at least 1 dose of randomized investigational product, CAP-1002 or placebo.

Note that the “as-treated” principle will be applied to all evaluations;(i.e., participants who receive a treatment other than the one assigned in the randomization list will be analyzed as belonging to the actual treatment group and not that assigned by randomization).

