9. GENERAL CONSIDERATIONS FOR DATA ANALYSES

Due to the dynamic nature of COVID-19 clinical practice and changing knowledge of relevant outcome measures, the SAP reflects recent changes in the understanding of the clinical meaningfulness of the efficacy outcomes. All analyses are prespecified because the blind has remained intact for this study.

The currently supported version of SAS software (9.4 or later) will be used to perform all data analyses. The actual SAS version used will be presented in the Clinical Study Report.

All data in the database will be presented in the data listings. Unless otherwise stated, all listings will be sorted by treatment group, subject number and assessment date/time.

Unless otherwise stated, continuous variables will be summarized using descriptive statistics including number of non-missing observations, mean, standard deviation, median, minimum and maximum values. Categorical variables will be summarized with frequency counts and percentages. The population size (N for sample size and n for available data) and the percentage (of available data) for each class of the variable will be presented.

In general, only data from nominal protocol scheduled visits will be included in the summary tables. They will be used in summary tables which are not “time specific”, for example,

summaries of maximum post dose values. Data from unscheduled visits will not be included in the summary tables but will be included in the listings.

The mITT analysis population will be the primary basis for all analyses in this study.

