10. STUDY POPULATION

All disposition, baseline and demographic, efficacy, and safety analyses will be conducted on the Intention-to-Treat (mITT) as treated population and displayed by treatment group.

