11. EFFICACY ANALYSIS

The modified Intent-to-Treat Population (as Treated) is defined as all enrolled and randomized subjects who received any amount of study treatment; the mITT population will be utilized for all efficacy analyses. All summary tables will be displayed by treatment arm.

This is a Phase 2 proof of concept study, so a hierarchical testing order will be specified, but p-values will be utilized for descriptive purposes even if a step in the hierarchy is not met and there will be no adjustment for multiplicity of analyses. In addition to the analysis by severity of COVID risk at baseline, additional subgroup analyses will be conducted on an ad-hoc basis and will be fully described in the clinical study report.

The primary analysis for each efficacy endpoint will be as follows, unless otherwise noted in the corresponding section. A Cox Proportional Hazards (PH) model will be utilized to characterize overall survival or time-to-event, correcting for baseline COVID severity risk score. This risk score will be calculated based on historical data and will include baseline characteristics of age, weight, sex, and presence of comorbidities. In addition, unadjusted Kaplan-Meier curves will be presented by treatment group and summary statistics will include estimates of median survival (and corresponding 95% confidence interval), minimum and maximum time, and the number of censored subjects. The overall survival time will be compared between the treatment arms using a log-rank test.

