12. SAFETY ANALYSIS

Safety will be evaluated from adverse events (including serious AEs and/or deaths), laboratory results, vital signs, study drug exposure, and concomitant medications. Descriptive statistics will be utilized to summarize these data and will be displayed by treatment arm.

The Intent-to-Treat Population (as Treated) is defined as all enrolled subjects who received any amount of study treatment will be utilized for all safety analyses.

Extra measurements (such as unscheduled or repeat assessments) will not be included in the descriptive statistics but will be included in subject listings.

All AEs, ECG outliers, and clinical laboratory outliers that occur following infusion of study medication will be included in the tabulations of AEs and outlier events, including episodes that occur at unscheduled evaluations.

In addition to the summary tables, safety data will also be presented in the individual subject listings.

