14. STATISTICAL ANALYSIS CHANGES FROM THE PROTOCOL

The analyses described are based on the final clinical study protocol CAP-1002-COVID-19-2 Amendment 2.4 dated August 23, 2021. This SAP supersedes the statistical considerations identified in the protocol.

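### All efficacy endpoints are analysed by product received, under an mITT label, and no analysis by randomised arm is planned

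*SAP*

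**What the plan says.** SAP Section 6 gives one definition that serves as both the mITT set and the safety set: subjects who were randomised and "received at least 1 dose of randomized investigational product, CAP-1002 or placebo". A note adds that the as-treated "principle will be applied to all evaluations", so that "participants who receive a treatment other than the one assigned in the randomization list will be analyzed as belonging to the actual treatment group".

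The rule is repeated where efficacy is concerned:

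- SAP Section 10: "efficacy, and safety analyses will be conducted on the Intention-to-Treat (mITT) as treated population and displayed by treatment group".
- SAP Section 11: "The modified Intent-to-Treat Population (as Treated) is defined as all enrolled and randomized subjects who received any amount of study treatment". This set is used for every efficacy analysis.
- SAP Section 9: "The mITT analysis population will be the primary basis for all analyses in this study".

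SAP Section 12 gives safety a set with a slightly different name: "The Intent-to-Treat Population (as Treated) is defined as all enrolled subjects who received any amount of study treatment".

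Protocol Section 9.3 bases all analyses on an mITT population but does not say how a subject's arm is assigned. The SAP states in Sections 1 and 14 that it supersedes the protocol's statistical considerations, so its rule governs.

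**The concern.** A randomised comparison is protected by the assigned arm. Grouping by product received gives up that protection for any subject given the wrong product and relies instead on the error being unrelated to prognosis. Blinding makes this plausible, although SAP Section 5 accepts that the pharmacist preparing the product may be able to tell the two apart. The risk score in SAP Section 11 uses age, weight, sex and comorbidities, so adjusting for it cannot cover unmeasured prognosis.

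An intention-to-treat label, even a modified one, ordinarily tells the reader that subjects stay in their randomised arm. Here it does not mean that.

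At stake is every efficacy estimate in SAP Section 11, including mortality, if a wrong-product administration occurs. The rule has to be settled before anyone knows whether it did: SAP Section 8.4 treats a change of analysis population after approval as a major deviation that must be justified in the study report.

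**Working it through.** **Is an as-randomised efficacy analysis planned anywhere?**

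- SAP Sections 6, 9, 10 and 11: one dosed set, as treated, with efficacy included by name in 10 and 11.
- SAP Section 7.3: leaves exploratory analyses undefined, so it plans nothing specific.
- SAP Section 14: says "The analyses described are based on the final clinical study protocol" and that the SAP takes precedence. It itemises no changes and adds no other analysis.
- Protocol Section 9.3: names mITT and is silent on arm assignment.

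The answer is no.

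**Does Section 6 keep the wrong-product subject at all?** Read literally, its requirement for a dose of the randomised product would leave that subject out, while its note keeps the subject in under the other arm. Sections 10.1 and 11 carry no such requirement, so the subject is kept. This is a point of wording only.

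**How far can one subject move an estimate?** The plan has no figure to reproduce: SAP Section 4 says there is no formal sample size calculation. From the documents come 1:1 allocation and about 30 per arm. The death counts are assumptions, shown over a range.

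Suppose d deaths per 30 in each arm as randomised, so the true-to-randomisation difference (CAP-1002 minus placebo) is 0. One placebo-randomised subject receives CAP-1002, so the as-treated arms are 31 and 29.

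- If that subject died: (d+1)/31 - (d-1)/29
- If that subject survived: d/31 - d/29
- Standard error of the difference, as randomised: sqrt(2 × p × (1-p)/30), with p = d/30

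| d | Subject died | Subject survived | Standard error |
|---|---|---|---|
| 3 | 4/31 - 2/29 = +6.0 points | 3/31 - 3/29 = -0.7 points | 7.7 points |
| 6 | 7/31 - 5/29 = 22.58% - 17.24% = +5.3 points | 6/31 - 6/29 = 19.35% - 20.69% = -1.3 points | 10.3 points |
| 9 | 10/31 - 8/29 = +4.7 points | 9/31 - 9/29 = -2.0 points | 11.8 points |

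If the error is unrelated to outcome, the subject died with probability d/30 and the average shift is zero. At d = 6: 0.2 × 5.34 - 0.8 × 1.33 = 0 to rounding. The same holds at d = 3 and d = 9.

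**With an assumed difference between arms.** Take 3/30 on CAP-1002 and 9/30 on placebo as randomised: difference -20.0 points, two-sided Fisher p = 0.104. Move one placebo-randomised subject to CAP-1002:

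- With an event: 4/31 v 8/29, difference -14.7 points, p = 0.204.
- Without an event: 3/31 v 9/29, difference -21.4 points, p = 0.054.

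**Cost of the alternative.** Keeping that subject in the placebo arm dilutes a real effect by about 1/30 = 3.3%.

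**The case against.** The strongest reply is that this may never matter. There is one infusion on Day 1, randomisation runs through the data capture system (SAP Section 5), and Protocol Section 6.2.1 requires records showing that each subject got the assigned product. A partial infusion does not change arm. The trial is a pilot with descriptive p-values and no multiplicity adjustment, so no confirmatory decision depends on the rule. In the equal-deaths table, every single-subject shift is below one standard error and the average is zero if errors are unrelated to outcome. The rule is also open: Sections 10 and 11 attach the as-treated wording to the population label itself.

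Most of this stands, and it limits the weight of the point. It does not supply the missing analysis. The SAP still sets a testing order and will judge proof of concept on these endpoints, and an unlikely event is no reason to prespecify the weaker grouping.

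Two further replies are fair. Since the protocol is silent on arm assignment, the SAP rule fills a gap more than it departs from the protocol, so its absence from Section 14 is a minor matter. And analysing dosed subjects by randomised arm does not restore a full randomised comparison, because untreated subjects are still excluded and replaced. That is a separate question.

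**Conclusion.** The concern holds. The SAP analyses all efficacy endpoints by product received, and neither document provides an efficacy analysis by randomised arm.

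The consequence is conditional. It is nil with no wrong-product subjects. For one such subject, under assumed equal death counts of 3 to 9 per 30, the mortality difference shifts by +4.7 to +6.0 points or by -0.7 to -2.0 points, against standard errors of 7.7 to 11.8 points. Systematic bias arises only if the error is related to prognosis, which blinding makes unlikely but does not exclude. The change should be made because it removes an unnecessary assumption at almost no cost; the point does not undermine the trial.

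**What to change.** Define two sets in SAP Section 6:

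1. **mITT:** randomised subjects who received any investigational product, analysed in the arm to which they were randomised. Use it for all Section 11 analyses and for the disposition and baseline tables of Section 10.
2. **Safety set:** the same subjects, grouped by product received. Use it for Section 12 and for exposure (Section 10.7).

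Then make the text agree:

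- **Section 6:** limit the as-treated note to the safety set, and drop the word requiring that the product be the randomised one.
- **Section 9:** make mITT the basis for efficacy and the safety set the basis for safety.
- **Sections 10 and 11:** remove the as-treated wording for efficacy. Name the set for protocol deviations (10.2) and concomitant medications (10.5); Section 12 counts the latter as safety data.
- **Section 12:** replace the intent-to-treat label with the safety set.
- **Section 14:** add one line recording how arm is assigned in each set.

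An as-treated efficacy analysis can stay as a sensitivity analysis, where it would show any dilution.

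The cost is a few words in these sections and separate planned-arm and actual-arm variables in the analysis dataset. No new data are needed. The statistical price is the dilution of about 3.3% per wrong-product subject. The edits should be made before unblinding.

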7. PLANNED ANALYSES

7.1 Final Efficacy Analysis for 30 Day Outcomes

Since a primary concern is not to add risk to subjects who are already considered to be at risk from the effects of COVID-19, the safety of each enrolled subject will be monitored by an independent Medical Monitor on an ongoing basis. Oversight of the protocol will be provided by an independent Clinical Events Adjudication Committee (CEC) and Data Safety Monitoring Board (DSMB). Stopping rules at the subject level and study level have been defined to ensure subjects are not exposed to significant risks and are outlined in Section 7.1 of the protocol.

In addition to the Medical Monitor, CEC, and DSMB oversight, the protocol also states: “Early analyses of the clinical data may occur and will include safety and efficacy”. However, only a review of safety data will be performed; there will be no interim analysis of efficacy.

7.2 Final Analysis

The final tables, listings, graphs, and data analyses will be conducted once all study participants have completed the study (through the Day 90 visit) and the clinical database has been locked.

7.3 Exploratory Analysis

All data available for analysis and described in Section 3.2 and data not specifically accounted for in Section 3.2 Endpoints may be used in exploratory analyses to be defined.

8. DATA PRESENTATION AND HANDLING

8.1 General Summary Table and Individual Subject Data Listing Considerations

Summary tables and listings will be prepared according to (ICH) Guideline E3.

In general, summary tables will be organized with respect to treatment group and presented as:

| CAP-1002 (N=00) | Placebo (N=00) | Total (N=00) |
|--------------------|-------------------|-----------------|
|--------------------|-------------------|-----------------|

Row entries in post text tables are made only if data exists for at least one subject (e.g., a row with all zeros will not appear). The only exception to this rule will apply to tables that summarize the study termination status of subjects (e.g., reasons for not completing the study). In this case, zeros will appear for study termination reasons that no subject satisfied.

The summary tables will clearly indicate the number of subjects to which the data apply and unknown or not performed are distinguished from missing data.

Adverse event preferred terms and body/organ systems and medical history conditions will be coded using the Medical Dictionary for Regulatory Activities (MedDRA®) dictionary Version 23.0. Concomitant medications will be coded according to the World Health Organization (WHO) Drug Global B3 March 1, 2020 dictionary.

Listings will also be sorted by treatment arm and subject number. Listings will also include visit number, visit date/time and days relative to the initiation of study treatment.

In general, missing data will not be imputed unless otherwise specified. Any imputed or derived data will be flagged in the individual subject data listings. Imputed data will not be incorporated into any raw or primary datasets. These data will be retained in derived analysis datasets.

8.2 General Summary Table and Subject Data Listing Format Considerations

The tables, figures and listings will be numbered using a decimal system to reflect main levels of unique tables and listings and sub-levels of replicate tables and listings with two digits per level (e.g., Table XX.YY.ZZ.).

1. The first level number will be consistent with the corresponding Clinical Study Report (CSR) appendix in which the tables or listings will appear. For example, the post text tables will appear in Appendix 14 (and will be numbered 14.XX.YY) and the individual subject data listings will appear in Appendix 16 (and will be numbered 16.XX.YY). The subject disposition table will be first in the first section of the report and will be numbered Table 14.1. The supportive subject data listing will be Listing 16.1. Any subset table will have the number Table 14.1.2, etc.
2. Table numbering will follow ICH E3 for Phase 1 CSRs. Subject disposition, baseline and demography and prior and concomitant medications tables should appear as the second level number (Table 14.1 series). Efficacy tables will occupy the next sub-level (Table 14.2 series – 14.2.1, 14.2.2 and 14.2.3, respectively). Safety tables will follow next (Table 14.3 series). Similar conventions will be applied to the subject data listings.
3. Each table and listing title will be complete, accurate and concise. The last line of the title will provide the analysis group being summarized (e.g., Intent-to-Treat Population).

4. If possible, variables being summarized, and statistics reported will appear in the left most column of a table. The next columns for (treatment groups) should report the data from left to right CAP-1002, Placebo, and study total; respectively.

8.3 Data Management

All data will be recorded by the site in individual source documents. An eCRF will be created by the data management group for recording of the required data in the study database. All eCRF information is to be filled in by site staff. If an item is not available or is not applicable, this fact should be indicated. Blank spaces should not be present unless otherwise directed.

The study monitor will perform source data verification of data entered into the eCRF and raise queries for correction by the site. The data entered into the eCRF will be subject to data validation checks for consistency and completeness by the data management group. Data queries will then be generated and sent to the investigational site for response before the database is locked and released for statistical analysis.

Database build, AE coding, medication coding, data cleaning will be conducted according to the Vantage Data Designs, Inc, CRO Data Management Plan for this specific study.

Derived datasets will be created using SAS® software. Data analyses and summary tables will be generated using the currently supported version at the time of data analysis (currently version 9.4).

